1	Mubende																		
	Wakiso																		
2	Bugiri																		
	Kayunga																		
3	Masaka																		
	Ndejje																		
4	Kasambya																		
	Mityana																		
5	Iganga																		
	Nagalama																		
6	Gombe																		
	Kiboga																		

Figure 2. Modified study schema, with post-randomization site and cluster assignments, and enrollment pauses for Ebola Virus Disease lockdowns in October-December 2022, and low anticipated enrollments during the holiday period.

Study Population

Eligibility Criteria

A. Site-level Inclusion Criteria

- Diagnoses ≥ 12 index TB cases/month based on 2021 Uganda DHIS2 TB surveillance reports
- Located outside Kampala District (as defined by the Kampala Capital City Authority Boundary)
- Located ≤ 180 km from Kampala City

B. Site-level Exclusion Criteria

- Site leaders decline to participate in the study

C. Patient-level Inclusion Criteria

- Index Persons with TB
 - Adults and children recorded as new TB cases in the TB treatment register
 - Residing ≤ 40 km from the clinic
- Contact Persons
 - Adults and children reporting ≥ 12 cumulative hours with the index case inside an enclosed space during the previous 3 months
 - Those sleeping ≥ 1 day or night under the same roof may be called “household” contacts.
 - Others not meeting this criterion may be called non-household “close” contacts.

D. Patient-level Exclusion Criteria

- Index Persons with TB
 - Lacking the mental capacity to consent to contact investigation procedures
 - Lacking contacts, as defined above under patient-level inclusion criteria
 - Diagnosed or referred for evaluation as a DR-TB patient (whether possible or confirmed)
 - Previously completed TB contact investigation within the last two months
 - Declining to refer close contacts for contact investigation procedures
- Contact Persons
 - Lacking the mental capacity to consent to contact investigation procedures
 - Currently taking treatment for active TB
 - Declining contact investigation procedures

Target Setting and Enrolment Sites

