- a) *Outcome definition:* Number of contacts who complete TB evaluation within 60 days (ctevalcomplete60) of index patient treatment initiation divided by the total number of contacts screening TB symptom positive (ctevaleligible). This will be an aggregate, cluster-level, exposure-specific (control versus intervention) measurement.
- b) *Outcome analysis:* Difference in log odds of the outcome between the intervention and control exposure periods using the Logit model (*n.b.*, this will be the same for all proportional outcomes)

Secondary Outcomes

- a. **Effectiveness** (*i.e.*, clinical effectiveness)
 - i. Proportion of contacts diagnosed with active TB (also known as the active TB treatment yield of TB contact investigation, or the number needed to screen):
 - a) *Outcome definition:* Number of contacts diagnosed with active TB (definitions below) and initiated on treatment within 60 days of index patient treatment initiation divided by the total number of contacts encountered.
 - (i) Microbiologically confirmed active TB: Diagnosed by a positive AFB-smear microscopy result, GeneXpert result, or other accepted *Mtb*-specific microbiologic test (*e.g.*, urinary LAM or mycobacterial culture)
 - (ii) Clinically confirmed active TB: Active TB diagnosed clinically, based on clinically diagnosed extra-pulmonary TB or a decision to initiate presumptively for active pulmonary TB.
 - b) *Outcome analysis:* As above
 - ii. Proportion of contacts initiating TB preventative therapy (TB preventative therapy yield of TB contact investigation):
 - a) *Outcome definition:* Number of TB contacts initiated on TB preventive therapy within 60 days of index patient treatment initiation divided by the total number of contacts eligible for TB preventive therapy
 - (i) Children under age 5
 - (ii) Persons living with HIV
 - (iii) Older adolescent (age ≥ 15 years and adult household and other close contacts with a positive TST and in whom active TB has been excluded by symptoms and/or testing)
 - b) *Outcome analysis:* As above
- b. **Public Health Impact** (*i.e.*, public health effectiveness)
 - i. Count of contacts diagnosed with active TB:
 - a) *Outcome definition:* Number of contacts diagnosed with active TB (definitions below) and initiated on treatment within 60 days of index patient treatment initiation
 - (i) Microbiologically confirmed, as defined above
 - (ii) Clinically confirmed, as defined above

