 - c) *Outcome analysis:* Difference in the natural log of the counts of the outcome between the intervention and control exposure periods using the Poisson model (*n.b.*, this will be the same for all count outcomes)
 - ii. Count of contacts initiating TB preventative therapy (TB preventative therapy yield of TB contact investigation):
 - a) *Outcome definition:* Number of contacts initiated on TB preventative therapy within 60 days of index patient treatment initiation

- b) *Outcome analysis:* As above
- iii. *Proportion of all TB cases among contacts:*
 - a) *Outcome definition:* Number of newly diagnosed TB cases who are contacts among all those TB cases, divided by the total number index TB patients
 - b) *Outcome analysis:* As above

Additional Outcomes

- a. **Efficiency** (i.e., the stepwise yield of contact investigation)
 - i. Proportion completing each step of the contact tracing cascade (for cases a(i) through a(vi) and for contacts b(i) through b(vii)), with the denominator the number eligible at the end of the previous step.
 - a) Proportion of index cases
 - (i) who were invited to contact investigation (count of all index patients in treatment registers),
 - (ii) who accepted the invitation (idxcons), and
 - (iii) who had at least one contact interviewed (_merge)
 - b) Proportion of reported contacts
 - (i) who were screened for TB symptoms (ctcons),
 - (ii) who were found to have TB symptoms (tbsymptoms),
 - (iii) who were evaluated for active TB based (ctevalcomplete),
 - 1. who were diagnosed with active TB (tbpositive),
 - a. who initiated TB treatment (within 2 months) (cttbrx combined with cttbrxstartdate),
 - (iv) who were found not to have active TB (as a proportion of those who had no symptoms (ctcons-tbsymptoms) plus those who had symptoms but were found not to have active TB (ctevalcomplete-tbpositive))
 - 1. who initiated TB preventative therapy (within 2 months) (ctipt combined with ctiptstartdate)
 - b. **Timeliness** (i.e., time to effective implementation)
 - i. Time to recruitment to contact investigation
 - a) *Outcome definition:* Days from index patient treatment initiation (idxrxstartdate) to case acceptance of contact investigation invitation among eligible cases (idxrecruitdate)
 - b) *Outcome analysis:* Difference in time-to-event between the intervention and control exposure periods using Survival analysis, n.b., this will be the same for all time-to-event outcomes)
 - ii. Time to contact screening visit

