This sequence of allocation restricted by sites will be determined through a two-stage random drawing during a public randomization ceremony held in Kampala, Uganda. A senior clinician representative of each health center (e.g., the TB focal person), the Health Facility Administrator-in-Charge, and the District Health Officer will be invited to attend a public randomization ceremony chaired by the Uganda NTLP Director. In the first, so-called “Cluster Stage”, health facilities will be divided into high-volume and low-volume strata for cluster assignments. Each health center representative will draw, without replacement, one ball labeled with the cluster designation, until all sites are assigned in paired clusters. In the second and final, or “Group Stage,” the two representatives of each cluster will assign one representative to draw, without replacement, 1 of 6 balls (labeled 1, 2, 3, 4, 5, 6) from an opaque bag to choose the group. Group 1 will be the first group to cross over, Group 2 the second to cross over, and so on. The sites will follow this cross-over sequence at equally spaced, 2-month intervals during the trial period, starting at the beginning of month 3.

Statistical Methods

For standardization purposes, the start of effective intervention exposure for clusters will be considered the first Monday of the next calendar week after the end of each 8-week transition period. This standardization will help fix the trial period slices and improve statistical efficiency for the within-period analyses. We will use a cluster-period mixed-effects logit model[5, 6] to assess differences between post-intervention and pre-intervention periods with regard to the proportion of contacts who completed TB evaluation within 60 days of index treatment initiation, the proportion of contacts diagnosed with active TB, the proportion of contacts initiating TB preventative therapy and proportion of all TB cases among contacts. We will use a cluster-period mixed-effects Poisson model[5, 6] to assess the difference between post-intervention and pre-intervention periods with regard to the count of contacts diagnosed with active TB and the count of contacts initiated on TB preventative therapy within and between periods. We will test for secular trends using both fixed and random effects. If secular trends are present, we will use a segmented regression model.

a. Dataset assembly, cleaning, and creation of new variables

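### The secondary outcome on the contact share of TB cases is divided by index patients, a denominator that does not match its label and need not contain the numerator, yet it is listed for a logit model

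*SAP*

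**What the plan says.** In the SAP, Secondary Outcomes, b. Public Health Impact, item iii is headed "Proportion of all TB cases among contacts". Its numerator is "Number of newly diagnosed TB cases who are contacts among all those TB cases", and this is "divided by the total number index TB patients".

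The model for this outcome is described in four places:

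- The analysis line under item iii only refers back to what stands above it. The nearest full statement above, under item i of the same group, is the Poisson model for counts.
- The primary outcome's analysis line gives the logit model and adds that "this will be the same for all proportional outcomes".
- Statistical Methods says "We will use a cluster-period mixed-effects logit model[5, 6] to assess differences between post-intervention and pre-intervention periods", and the list of outcomes that follows ends with "initiating TB preventative therapy and proportion of all TB cases among contacts".
- Section c, Intervention Effect Analysis, replaces odds ratios by proportion ratios when the proportion exceeds 15%. It assigns the proportion models to implementation and clinical effectiveness, and Poisson to counts, labelled public health effectiveness.

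On who is an index patient, Eligibility Criteria C takes any new case in the TB treatment register who lives within 40 km. Criteria D excludes, among others, index persons who "Previously completed TB contact investigation within the last two months".

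**The concern.** The label and the definition describe different quantities. A share of all TB cases has every case in the denominator, so it lies between 0 and 1 and suits a logit model. Contact cases per index patient is a ratio of two counts. Nothing in the definition makes the first count part of the second.

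The reported level and the odds ratio therefore may not be those of the named share, and two analysts could compute different figures from the same data. There are also two practical problems:

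- **Individual-level analysis.** SAP 3.1.2 b moves to this if secular trends are present. With index patients as the denominator there is no 0/1 outcome per unit, because one index patient can yield several contact cases.
- **Aggregated analysis by site and month.** The ratio can exceed 1 in a small cell, where a logit is undefined.

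**Working it through.** **Planned figure.** The documents give no expected value, effect size or power for this outcome, so there is nothing to reproduce. The algebra is exact, but the size rests on assumptions.

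**Algebra.** Let C be contact cases, I index patients and r = C/I, with subscript 0 for control and 1 for intervention. Suppose the two groups are counted separately.

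- Named share: C/(C+I) = r/(1+r). Its odds are C/I = r, so its odds ratio is r1/r0.
- Ratio as defined, treated as a proportion in a logit: its odds are r/(1-r), so the odds ratio is (r1/r0) × (1-r0)/(1-r1). The extra factor is (1-r0)/(1-r1).
- Level: r divided by r/(1+r) is 1+r, so the reported level is too high by a relative factor r.
- If r1 = r0, both odds ratios are 1.

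If every contact case is also counted in I, C/I is already a true proportion and the extra factor disappears.

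**Inputs.**

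- Contacts per index patient: 781/273 = 2.86 (SAP, Power and sample size calculation).
- TB yield among household members: 3.3% to 4.5% (Protocol, Background).
- Evaluation completion: 0.2 rising to 0.4 (SAP, Summary of the power section). The same section also uses 0.4 to 0.6.
- Assumption: r = 2.86 × yield × completion. This applies a household yield to all contacts and scales it by completion, so it shows the order of size and is not a forecast.

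**Results.**

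| Yield | Completion | r0 | r1 | r1/r0 | OR as defined | Excess |
|---|---|---|---|---|---|---|
| 3.3% | 0.2 to 0.4 | 0.0189 | 0.0378 | 2.00 | 2.04 | 2.0% |
| 4.5% | 0.2 to 0.4 | 0.0257 | 0.0515 | 2.00 | 2.05 | 2.7% |
| 3.3% | 0.4 to 0.6 | 0.0378 | 0.0566 | 1.50 | 1.53 | 2.0% |
| 4.5% | 0.4 to 0.6 | 0.0515 | 0.0772 | 1.50 | 1.54 | 2.8% |

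First row in full: 2.00 × (1-0.0189)/(1-0.0378) = 2.00 × 0.9811/0.9622 = 2.04.

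**Level.** At r = 0.0515 the share is 0.0515/1.0515 = 0.0490, a difference of 0.25 percentage points. If every contact were evaluated, r would be 2.86 × 0.033 = 0.094 to 2.86 × 0.045 = 0.129, against shares of 0.086 to 0.114.

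**Larger ratios (assumed, not from the documents).** For r from 0.10 to 0.20 the odds ratio is 2.00 × 0.90/0.80 = 2.25 against 2.00. For 0.15 to 0.30 it is 2.00 × 0.85/0.70 = 2.43 against 2.00.

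**If the 15% rule were applied.** The reported r1/r0 exceeds the ratio of shares by (1+r1)/(1+r0). For r from 0.10 to 0.20 that is 2.00 against 1.83.

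**Small cells.** The SAP's 11 index patients per 8-week block give 5.5 per 4-week month. With Poisson counts, simulation puts the chance that C exceeds I in a clinic-month at about 0.1% for r = 0.026 and 0.9% for r = 0.129. At the pre-trial volume (273/12/2 = 11.4 per month) it is below 0.1%.

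**The case against.** The best defence is that the numerator may already lie in the denominator. Index persons are new cases in the treatment register, and the process-measure definitions for diagnosis and treatment use that same register for contacts. A treated contact can therefore be a new registered case and possibly an index patient. This stands: the SAP does not exclude it. But it does not state it either, and the label still differs from the definition.

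A reader might go the other way and infer from the two-month exclusion that most contact cases are kept out of the denominator. The documents do not support that. The criterion is listed for index persons, can be read as covering a patient whose own contacts were already investigated, and comes with no figure.

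The second defence is that the model may be Poisson. The reference back in item iii and the scope in Intervention Effect Analysis allow that reading. A Poisson model with index patients as offset would estimate r1/r0, which is free of the distortion. Statistical Methods, however, names this outcome in the logit list, so the conflict is on the page.

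Third, the distortion is small. That stands too. A reader might infer a material exaggeration from an example such as 2.25 against 2.00, but that needs ratios about four times those implied by the documents' figures for completion of 0.2 to 0.4. Its upper value also exceeds the 15% threshold, so if that rule covers this outcome a proportion ratio would be reported instead.

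**Conclusion.** The definition is wrong as written: its denominator contradicts its label and is not guaranteed to contain the numerator, while the SAP lists the outcome for a logit model. Severity is low.

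The documents do not support the stronger statements that the numerator lies wholly outside the denominator or that the effect will be materially overstated. The distortion arises only if contact and index cases are counted separately and the logit is used. It is then about 2% to 3% on the odds ratio under the assumed contacts per index patient, yield and completion, and larger only if the ratio is much larger. Under no effect, with separate counting in both periods, there is no bias, so this does not by itself create a false effect. One secondary outcome is concerned; the primary outcome and sample size are not.

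**What to change.** Choose one of two equally valid definitions:

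1. Keep the label and the logit. Define the denominator as index patients plus contacts diagnosed with TB at the site in the period, each person counted once. Each case is then either a contact or not, which also serves the individual-level analysis.
2. Rename the outcome contact cases per index patient and use the Poisson model with the log number of index patients as offset.

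Either way, state whether a diagnosed contact also counts as an index patient, and make the outcome definition, Statistical Methods and Intervention Effect Analysis name the same model, including whether the 15% rule applies here.

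The cost is one line of definition and matching edits to the model statements. Counting each person once requires identifying diagnosed contacts among the registered cases; the SAP already plans to validate effectiveness endpoints against the treatment registers. Under the first option the reported proportion and odds ratio would be slightly smaller than under separate counting. The change should be made before the outcome is tabulated by exposure period.

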 - b) Cumulative proportion (Number of contacts who complete TB evaluation within 60 days of index patient diagnosis divided by the number of total contacts referred for TB evaluation, defined as providing sputum, undergoing chest radiography, or undergoing evaluation by a clinician at the TB diagnostic unit)
2. Cumulative TB diagnostic yield among all contacts identified, within 60 days

Secondary Outcomes

1. Proportion completing each step of the contact tracing cascade, with the denominator the number eligible at the end of the previous step.
 - (a) Proportion of eligible index cases
 - (i) who were invited,
 - (ii) who accepted invitation,
 - (iii) who identified at least one contact
 - (iv) who had at least one contact interviewed
 - (v) who initiated TB treatment (within 2 months), and (vi) who completed TB treatment (within 12 months)
 - (b) Proportion of all named contacts

- (i) who were reached,
- (ii) who screened positive, (iii) who had sputum collected, (iv) who had sputum delivered, (v) who had sputum tested, (vi) who were diagnosed,
- (vii) who initiated treatment (within 60 days of diagnosis)
 - 1. for active TB disease
 - 2. for latent TB infection
- (viii) who completed treatment (within 12 months)
 - 1. for active TB disease
 - 2. for latent TB infection
- 2. Timeliness of contact investigation (Median days from case diagnosis)
 - (a) Time to case invitation
 - (b) Time to contact screening visit
 - (c) Time to contact testing, radiographic evaluation, or clinical evaluation
- 3. Pre-specified sub-group analyses for all primary and secondary outcomes
 - (a) Subgroup
 - (i) Adults
 - (ii) Older Children (age 5-14)
 - (iii) Young Children (under age 5) (iv) Persons living with HIV
 - (b) Contact type
 - (i) Household
 - (ii) Non-household close contacts
 - 1. Workplace
 - 2. Social
 - (c) Clinic site /community

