Contact investigation cascade process measures for index cases (the variable names used in the CommCare database specified in parentheses below).

1. **Invited:** Cases offered TB contact investigation (idxcons)
2. **Accepted:** Cases agreeing to TB contact investigation (idxcons), as defined by index patient interview date (idxrecruitdate)
3. **Encountered contacts:** Encountering ≥ 1 contact per index patient for TB contact investigation (ctinterviewdate),
4. **Reached contacts:** ≥ 1 contact successfully screened for TB symptoms, as defined by contact interview date (ctinterviewdate in conjunction with tbsymptoms)
 - a) *Reached household contacts:* Cases with ≥ 1 household contact interviewed
 - b) *Reached other close contacts:* Cases with ≥ 1 non-household contact interviewed

TB evaluation and treatment cascade process measures for TB contacts:

1. **Contacts Encountered:** Contact encountered by Community Health Worker (cascade may be stratified by household contact or non-household close contact status) (ctcons)
2. **Screened TB Symptom Positive:** Contacts reporting ≥ 1 of the following (tbsymptoms):
 - a. Cough of any duration (ctcough), with or without sputum production
 - b. Fever (including subjective fever) or chills (ctfever)
 - c. Night sweats (ctnightsweats)
 - d. Weight loss (estimated to be) ≥ 3 kg (ctweightloss), or poor weight gain among children aged <5 years (both subjective) (ctchildpoorweightgain)
 - e. Child <5 who is tired or less playful (subjective) (ctchildtired)
 - f. Child <5 who has noisy breathing or wheezing (ctchildwheezing)

Contacts who are “Screened TB Symptom Positive” are also considered “possible TB patients.”

3. **Sputum collected and delivered:**
 - a. *Sputum collected:* Sample logged as collected by a CHW (ctsputcommunitycollect)
 - b. *Sputum received:* Sample logged as arrived in the laboratory (ctsputreceived)
4. **TB Evaluation Completed:** Contacts meeting ≥ 1 of the following criteria:

- a. **TB Testing Completed:** Meeting ≥ 1 of the following criteria, as defined by analysis result/date recorded by CHW (ctspputanalysisdate):
 - i. Completed sputum smear microscopy exam (≥ 1 sample examined) (ctsmearrsIt)
 - ii. Completed GeneXpert (Xpert) testing (≥ 1 sample examined) (ctxpertrsIt)
- b. **Completed TB Clinical Evaluation:** Evaluated by a clinician, as documented by a community health worker at one of the study sites (ctevaldate, cttbdiagnosedclinic)

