 - a) *Outcome definition:* Days from index patient treatment initiation (idxrxstartdate) to contact TB screening (ctinterviewdate)
 - b) *Outcome analysis:* As above
 - iii. Time to completion of contact evaluation
 - a) *Outcome definition:* Days from index patient treatment initiation (idxrxstartdate) to completion of contact evaluation, defined as completion of sputum testing (ctspputanalysisdate), or, if sputum testing not completed, completion of clinical evaluation or chest radiography (ctevaldate), whichever comes first.

- b) *Outcome analysis:* As above
- c. **Equity** (i.e., pre-specified, stratified analyses for all primary and secondary outcomes)
 - i. Clinic site/community subgroups
 - a) *Outcome definition:* Days from index patient treatment initiation to completion of contact evaluation, defined as completion of sputum testing, or, if sputum testing is not completed, completion of clinical evaluation or chest radiography, whichever comes first.
 - b) *Outcome analysis:* As for the underlying outcome above, including both restricted and within-group analyses
 - ii. Individual patient subgroups
 - a) *Outcome definition:* Strata defined below
 - (i) Age (ctage)
 - 1. Adults (age ≥ 18)
 - 2. Adolescents (age 10-17)
 - 3. Older Children (age 5-9)
 - 4. Young Children (under age 5)
 - (ii) HIV status, at baseline (cthiv0) or clinic follow-up (cthivclinic)
 - 1. Persons living with HIV
 - 2. Persons not living with HIV
 - 3. Unknown HIV status
 - (iii) Contact type
 - 1. Household contact
 - 2. Non-household close contact
 - b) *Outcome analysis:* As above

Power and sample size calculation

Power and sample size calculations for the proposed stepped-wedge, cluster-randomized trial assume two levels of clustering. Representing the first level of clustering (rho-alpha) at intraclass correlation coefficient (ICC) level 1 are index TB patients nested within clinics and representing the second level of clustering (rho-beta) at ICC level 2 are contacts nested within index TB patients. According to pre-trial empirical data collected at 12 clinics between 1st January 2022 and 6th March 2022, there were 781 total contacts of 273 index TB patients, giving an average of 22.7 index TB patients in each of the 12 clinics, and 2.86 contacts per index TB case during a 2-month block period.

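### The SAP's Timeliness rule lets a later sputum result override an earlier clinician or X-ray evaluation, which disagrees with its own definition of completed TB evaluation

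*SAP*

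**What the plan says.** **When evaluation counts as complete.** SAP, Definitions of process measures, item 4 (TB Evaluation Completed) sets the rule as "Contacts meeting ≥ 1 of the following criteria". The criteria are sputum testing (dated by ctspputanalysisdate), clinical evaluation ("Evaluated by a clinician, as documented by a community health worker at one of the study sites", with ctevaldate) and chest radiography. No order is given, and no separate radiography date is listed. The protocol's primary outcome 1b is likewise unordered: "defined as providing sputum, undergoing chest radiography, or undergoing evaluation by a clinician at the TB diagnostic unit". Its secondary timeliness outcome 2(c) lists testing, radiographic evaluation and clinical evaluation as alternatives without ranking them.

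**When completion is dated.** SAP, Additional Outcomes, b. Timeliness, iii takes the sputum analysis date first and then turns to the other components: "or, if sputum testing not completed, completion of clinical evaluation or chest radiography (ctevaldate), whichever comes first". The outcome definition under c. Equity, i repeats this conditional without the variable names.

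**How it is analysed.** Time-to-event outcomes go into survival models, specified as mixed-effects parametric models (mestreg) under Intervention Effect Analysis.

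**Primary outcome.** The numerator is "Number of contacts who complete TB evaluation within 60 days (ctevalcomplete60) of index patient treatment initiation". The SAP does not spell out how the component dates are compared with day 60.

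**The concern.** The SAP says what completes an evaluation and, separately, when it was completed. The two rules should give the same event, and on the natural reading of Timeliness iii they do not. A contact whom a clinician sees on day 10, with a sputum result on day 25, has met the definition on day 10 but is dated day 25.

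The rule also looks ahead. Whether the day-10 evaluation is the event depends on whether a sputum test is completed afterwards. Until that result is entered the contact's time is 10 days; once it is entered the time becomes 25. A survival model needs an event that can be recognised when it happens.

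The main thing at stake is the validity of one Additional outcome and of the Equity item that borrows its definition. There is a secondary exposure. Timeliness iii is the only SAP text that combines the component dates, so a programmer building ctevalcomplete60 could reuse it. Records near the 60-day limit are plausible, because community health workers keep trying until the two-month refill visit (SAP, Evidence-based Practice).

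**Working it through.** The plan states no figure for this point, so there is none to reproduce. The check compares the two rules.

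**Rules.** Let S be the day of the sputum result and C the day in ctevaldate, both counted from idxrxstartdate.

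- Sputum-first (natural reading of Timeliness iii): T = S if sputum testing was completed, otherwise T = C.
- Earliest component (follows from process measure 4): T = min(S, C) over the components done.
- Gap between the rules: S − C if both exist and C is before S; otherwise 0.

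**Example records (days chosen for illustration).**

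| Sputum result | Clinician/X-ray | Sputum-first | Earliest | Done by day 60? (sputum-first / earliest) |
|---|---|---|---|---|
| 25 | 10 | 25 | 10 | yes / yes |
| 70 | 20 | 70 | 20 | no / yes |
| 15 | 30 | 15 | 15 | yes / yes |
| none | 20 | 20 | 20 | yes / yes |
| 70 | none | 70 | 70 | no / no |

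The rules differ only when a clinician or X-ray evaluation precedes a sputum result. They change 60-day status only when day 60 falls between the two.

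**Scope of the closing words.** If the last phrase of the sentence covers only clinical evaluation and radiography, it has little to choose between, because both are dated by ctevaldate. If it covers all three components, it yields the earliest-component rule and the condition about sputum not being completed is redundant. On either reading one part of the sentence does almost no work.

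**Size of a shift in time (assumed inputs, none in the documents).** Take contacts first seen by a clinician on day 5 in both periods, some of whom have a sputum result 7 days later. Mean time under sputum-first = 5 + share × 7.

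- Shares 0.30 control, 0.70 intervention: 7.1 and 9.9 days, an artefact of +2.8.
- Shares 0.40 and 0.50: 7.8 and 8.5, +0.7.
- Shares 0.70 and 0.30: 9.9 and 7.1, −2.8.

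The earliest-component rule gives 5.0 in both periods each time. The sign follows the assumed shares.

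**Size of a shift in the primary proportion, only if the sputum-first date were used for it.** Let q be the share of symptomatic contacts with a clinician or X-ray evaluation by day 60 and a sputum result after it. Observed proportion = p − q. Take p = 0.20 and 0.40 from SAP Table 2 (difference 0.20, ratio 2.00), with q assumed:

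| q control | q intervention | Proportions | Difference | Ratio |
|---|---|---|---|---|
| 0.01 | 0.01 | 0.19, 0.39 | 0.20 | 2.05 |
| 0.01 | 0.03 | 0.19, 0.37 | 0.18 | 1.95 |
| 0 | 0.05 | 0.20, 0.35 | 0.15 | 1.75 |
| 0.03 | 0.01 | 0.17, 0.39 | 0.22 | 2.29 |

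Again the direction depends on q, which the documents do not give.

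**The case against.** The best defence is that the sentence ends by asking for whichever component comes first, which can be read as the earliest-date rule. That reading is available. It leaves the condition before it without a purpose, however, and two programmers could derive different dates from one record, so the ambiguity is itself a defect.

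A reader might go further and infer that the rule contradicts the primary outcome. The documents do not support this. Timeliness iii belongs to an Additional outcome, and nothing links it to ctevalcomplete60. Each component can be checked against day 60 separately, without a combined completion date, and process measure 4 names dates for sputum testing and clinical evaluation.

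A reader might also infer that the rule penalises the intervention, since the video and the riders promote sputum testing. This is not established either. The protocol's Interventions table places clinical evaluation after sputum collection, testing and results. It refers symptomatic children under 5 and contacts who produce no sputum, for whom the clinic visit may replace sputum testing, and then the rules agree. Riders carry sputum to the laboratory and also bring contacts to the clinic, so the affected group could grow or shrink after crossover.

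**Conclusion.** The point holds as an inconsistency within the SAP. On its natural reading, the dating rule in Timeliness iii and Equity c.i gives completion times that disagree with the SAP's definition of completion and with the protocol's unordered timeliness outcome. It also makes an event time depend on a later event.

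The affected contacts are those with a clinician or X-ray evaluation before a sputum result, and the shift for each equals the lag between the two. Without their frequency or lag, no size or direction of bias between periods can be stated; the worked figures show only the mechanism. No error in the primary outcome is shown. What remains there is a derivation that the SAP leaves unwritten, and the only nearby text that combines the dates is the ambiguous one. The verdict rests on taking the sputum condition as operative.

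**What to change.** In Timeliness iii and in Equity c.i, delete the condition about sputum testing not being completed. Define the completion date as the earlier of ctspputanalysisdate and ctevaldate, using whichever is present, and note that ctevaldate serves for both clinician evaluation and radiography, since no separate X-ray date is documented. Add that ctevalcomplete60 = 1 when this earliest date is within 60 days of idxrxstartdate, so that the primary and Timeliness outcomes agree. Time to sputum result can be reported separately as a descriptive measure if it is of interest.

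The cost is two edits of SAP wording, one added sentence and a line of code. Both variables are already named in the SAP, so no new data collection is needed.
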